## **6.4 Albumin**

### **6.4.1 Use of Albumin in the HepQuant SHUNT Test**

For the intravenous 13C-CA dose, exactly 5 mL of the 13C-CA intravenous solution are mixed with 5 ml of the albumin solution (25% w/v human serum albumin, Albutein®-25 from Grifols Therapeutic, Inc, BLA 102478 – NOTE that the vial of albumin contains 20 mL; only 5 mL is added to the 13C-CA in the syringe, 15 mL is discarded). The 13C-CA/Albumin mixture is administered intravenously through the indwelling intravenous catheter over 1 minute by the nurse administering the test. The 4D-cholate/flavored solution is administered orally simultaneously.

### **6.4.2 Reported Reactions to Human Serum Albumin**

#### **6.4.2.1 Hypersensitivity**

Albumin is given with the 13C cholate that is given intravenously. Albumin is a protein which is a normal part of your blood. In rare cases, hypersensitivity reactions to albumin have occurred. Some things that happen during any hypersensitivity reaction are:

- rash
- having a hard time breathing
- wheezing when you breathe
- sudden drop in blood pressure
- swelling around the mouth, throat, or eyes
- fast pulse
- sweating

- severe reactions are very rare (<0.01%; less than one chance in 10,000) but a severe reaction (called anaphylaxis) can lead to profoundly low blood pressure and even death.

Rare Hypersensitivity Reactions have been reported to human albumin preparations and include anaphylaxis or anaphylactoid reactions, fever, chills, rash, urticaria, pruritus, angioneurotic edema, and erythema or flushing.

#### **6.4.2.2 Risk of Transmissible Agents**

Because human albumin is prepared from pooled human plasma, there is a potential to pass human viruses (e.g., hepatitis viruses, HIV) and may carry a risk of transmitting Creutzfeldt-Jakob disease (CJD) or its variant CJD (vCJD). Through donor plasma screening and special procedures, like pasteurization to remove or inactivate any possible causes, reduce, but do not entirely eliminate the risk of transmission of disease causing agents. Nonetheless, the risk of transmission of viral disease with plasma-derived human albumin is considered extremely low. No cases of transmission of HBV, HCV, or HIV have been documented following use of commercially available human albumin. There are no documented cases of CJD or vCJD transmitted through plasma-derived preparations (including plasma-derived human albumin); the theoretical risk for disease transmission of CJD with commercially available human albumin is considered extremely low.

However, no purification method has been shown to be totally effective in removing the risk of viral infectivity from plasma-derived preparations and because new blood-borne viruses or other disease agents may emerge which may not be removed or inactivated by current manufacturing processes, the risks of human albumin are not entirely known.

### **6.5 Intravenous Catheter**

Placing the indwelling intravenous catheter will cause minor pain and discomfort. With any blood draw there is a small risk of hematoma and a very small risk of a blood clot (1 in 100) or infection (1 in 1000). Over 1500 HepQuant SHUNT tests or the prototypical dual cholate research tests have been performed on over 600 individuals and most had the test multiple times. There has never been an adverse event - the risk from the test is

very small. A questionnaire will be completed by the subject at each of the testing periods to log their experience and tolerability of HQ tests (Appendix C).

## **6.6 Other**

### **6.6.1 Data Security**

Data Security: HepQuant study data will be collected and entered by the site staff into OmniComm TrialMaster Electronic Data Capture system. Additionally, HepQuant test and analytic data will be entered by HepQuant into EXCEL, ACCESS or REDCAP databases on HepQuant's HIPAA-compliant and encrypted servers that have been configured for 21CFR11 compliance.

HepQuant will transfer test results of the HQ shunt test to Gilead. The corresponding studies will be linked by de-identified study IDs.

The technology used for backing up the HepQuant file servers is Veeam. Backups run every 12 hours and are stored on a dedicated storage appliance. Onsite backups are retained for 90 days before expiring and being over written. All backups are stored with AES 256 encryption. Every night a backup copy is sent offsite to a secure datacenter in Arizona. Backups are retained in Arizona with the following schedules:

- 180 Daily backups
- 26 Full Weekly backups
- 24 Full Monthly Backups (First Sunday of the month)
- 16 Quarterly backups (First Sunday of the quarter)
- 5 Annual backups

Backup data replicated offsite is encrypted in transit and has hardware level encryption at rest.

### **6.6.2 Data Security Procedures**

#### Storing and Securing Collected Data

- Chromatograms and associated peak areas are printed out during each LCMS analytical run and are considered the official raw data.

- Electronic copies (Agilent ChemStation software files) of the raw data from each run are stored on the local permanent disk storage (C drive) on the controlling computer attached to the LCMS system.

The ChemStation sequence used to direct the instrument is named for the day of the run (year as XX, month as XX, day as XX) and the analyst's initials. For example, the sequence of May 22, 2017, performed by [name] is named "170522 [name]" and the raw data generated from that sequence is automatically stored by ChemStation in a folder of that same name within the folder "C:\Chem32\1\data\". The sequence may be initiated to test system suitability or other parameters and only the first vial (system suitability standard) is injected and then the sequence is stopped if required (For example, the system suitability standard fails or the macro is not set up correctly). Each time the sequence is initiated a new subfolder is created. The subfolder that is created when the full sequence is completely executed is considered the run raw data set and at the completion of the run, it is renamed "XXXXXX" the date of the run. For example, the run Raw Data set would be "170522".

- During each run, a macro within Agilent Chemstation simultaneously generates in the folder "C:\Chem32\CORE\" a file called "rcvdata" containing a subset of the raw data (samples injection file #, injection time, vial #, sample name, injection #, peak retention time, peak area). After each run this raw data subset file is saved with a new name "rcvdata XXXXXX" with the same date as the raw data folder.
- For example, this file would be "rcvdata 170522". The "rcvdata XXXXXX" file is transferred to the analyst's encrypted laptop and used in the analysis to generate standard curves, QC results, and patient testing results.
- These data and folders, as well as all other laboratory data collection and analysis software on all the laboratory computers are only accessible when logged in by an authorized analyst. Each analyst is required to log in with a unique user name and unique password.

#### Backing Up Data

- After each run the raw data folder, "XXXXXX" is backed up by transferring it by the secure DSL directly from the C drive to the secure HepQuant server at RFC (Z drive). The raw data folders are also periodically backed up by transferring them to

read only DVDs that cannot be overwritten. These DVDs are then securely archived.

- After each run, the raw data subset file “rcvdata XXXXXX” is backed up by transferring it by the secure DSL directly from the C drive to the secure HepQuant server at RFC (Z drive).
- The secure server at RFC (Z drive) is itself backed up every night by CyberTrails to their secure server in Arizona.

#### Recovery of Data Backups

- When raw data backed up on the secure HepQuant server at RFC (Z drive) needs to be recovered, either for new analysis, supporting documentation, laboratory administration or integrity verification and validation, the raw data will be recovered from the secure HepQuant server at RFC (Z drive) via the secure DSL.
- Prior to transfer, the raw data folder, “XXXXXX”, on the Z drive will be saved with the new name “XXXXXX recover” and this folder will be transferred via the secure DSL to the laboratory LCMS computer folder which contains the original data.
- The reprocess function of Agilent Chemstation will then be activated on the file “XXXXXX recover” so that the macro generates a new raw data subset file and this file then will be saved with the name “rcvdata XXXXXX recover”.

#### Validation of Data Backups

- At intervals, dependent on project requirements, data backed up to the remote HepQuant server at RFC (Z drive) will be retrieved solely for the purpose of testing their completeness and integrity for validation of the data backup process.
- The SOP 001101 Form: “Laboratory Data Backup Validation Form” must also be completed by appropriate members of the validation team.
- On the form, paste screenshots of the file properties of the original raw data file folder and a recovered version of the raw data file folder and validate that the

recovered file folder is the same size as the original and contains the same number of files and subfolders.

- Open the “rcvdata XXXXXX recover” file and label every row of data as “recover” to distinguish it from the original data. Copy and paste the peak areas from the original “rcvdata XXXXXX” onto a new column and perform a test for equality [ =IF (recover area = original area, TRUE, FALSE)] and check that all values return a result of TRUE to validate that peak areas of the file “rcv data XXXXXX recovery test” match original peak areas.
- Transfer of the “rcvdata XXXXXX recover” file will be to an analyst’s encrypted laptop and used it to generate standard curves and QC results. Validate that standard curves generated from the “rcvdata XXXXXX recover” match the original data standard curves in linearity (R2), slope, and back-calculated values. Validate that QC results values generated from the “rcvdata XXXXXX recover” match the original data QC results values.

### **6.6.3 Management of Abnormal Test Results**

HepQuant will review all HepQuant SHUNT test results but will not distribute results to investigators, coordinators, GILEAD study personnel, primary care physicians, care providers, or subjects and no treatment or management decisions will be made on the basis of the HepQuant SHUNT results.

### **6.6.4 HepQuant Study Versus Gilead Clinical Trial**

The HepQuant Study encompasses only the administration of the HepQuant SHUNT test, use of the HepQuant SHUNT Liver Diagnostic Kit, and monitoring of the test and test outcome. We do not anticipate any additional risks or issues related to the HepQuant SHUNT test other than those described above. AEs, SAEs, and SUSARs related to the HepQuant SHUNT test will be evaluated by HepQuant and reported by HepQuant to the appropriate regulatory authorities, including local IRBs and FDA and Gilead drug safety.

## **6.7 Pregnancy Protocol**

Because cholates are naturally occurring with a pool size in humans of 1 to 5 g, the 20 and 40 mg doses of labeled cholates used in the HQ tests are unlikely to be harmful to a fetus. However, the effects of these compounds on the fetus are not definitively known.

Subjects will be co-enrolled in a placebo-controlled Gilead clinical trial of selonsertib. Subjects found to be pregnant during the Gilead clinical trial must discontinue study drug immediately. In this case, the subject must also stop participation in the HepQuant study.

It is recommended that all participants use a reliable form of birth control throughout the study. Double contraception using hormonal plus barrier methods is required. Hormonal birth control pills, intrauterine device (IUD), DepoProvera, Norplant, barrier methods (condom or diaphragm) plus a spermicidal agent, surgical sterilization, and complete abstinence are examples of reliable methods of birth control. Study participants will comply with the pregnancy precautions, and use one of the approved contraceptive methods, if applicable, as specified in the clinical protocols.

## **7.0 Potential Scientific Problems**

### **7.1 Potential Interfering Substances in Laboratory Assay**

#### **7.1.1 Assay Performance**

Use of concomitant medications could theoretically present potential interference in serum cholate measurement. The liquid chromatography-mass spectrometry (LCMS) technique used to measure cholate levels was validated according to FDA guidelines [66] for selectivity, accuracy, precision, recovery, stability, and freedom from interferences by serum components or medications. Freedom from interference was tested on blanks and at the LLOQ for each analyte with a number of metabolites and medications including: Bilirubin, Cholesterol, Carbamazepine, Oxazepam, Diazepam, Nordiazepam, Lorazepam, Temazepam, Flunitrazepam, Nitrazepam, Clonazepam, Alprazolam, Ephedrine, Codeine, Diphenhydramine, Nortriptyline, Propoxyphene, d-Amphetamine, d-Methamphetamine, Phenylpropanolamine, Phenmetrazine, Caffeine, Phencyclidine, Imipramine, Spironolactone, Furosemide, and dl-Propranolol. There was no interference at the

concentrations tested which were above those usually observed in patient serum samples.

## **7.2 Potential Complicating Medical Issues**

### **7.2.1 Concomitant Medications**

There are no known interactions of drugs or medications with the cholates used in the HepQuant SHUNT test.  $\beta$ -blockers or ACE inhibitors could affect the blood flow to the liver, so subjects who are currently taking either a beta blocker or an ACE inhibitor will be asked to delay taking their normal dose the morning of their testing. They can take the morning dose of these medications immediately after the 90 minute sample for the HepQuant SHUNT test is obtained. Delaying these medications could cause a temporary elevation in blood pressure but the risk would be minimal, similar to that of subjects who delay doses of medications in everyday life.

### **7.2.2 Associated Conditions**

Subjects with serious intercurrent medical or surgical illness, such as acute myocardial infarction, acute cerebral hemorrhage, sepsis, or other immediate life-threatening illness will be excluded. Subjects with extensive resection of large segments of small intestine (short gut) or severe gastroparesis might not be able to absorb the oral dose of 4D-CA and are excluded.

## **7.3 Potential Interaction between Cholate and Study Drugs**

Cholate, especially in the low doses used in the HepQuant SHUNT test, does not interfere with hepatic metabolism. Given these considerations there would be no suspected interaction between study drugs and cholate.

## **8.0 Data Analysis and Statistics**

### **8.1 Sample Size Calculation**

An important offshoot of our prior serial studies of the HepQuant SHUNT test was defining an average standard deviation for  $\Delta$ DSI (average SD of  $\Delta$ DSI = 3.5) that could

be used to determine sample sizes. The following table demonstrates the sample sizes required to detect a range of changes in DSI at 80% power or higher – for the case of the NASH trials. A sample size of 60 total subjects (N in following table), well below the size of our projected number of evaluable NASH patients could provide sufficient power to detect a difference in the  $\Delta$ DSI of 2 to 3.

Actual Power	N1	N2	N	<math>\Delta</math>DSI	<math>\sigma</math>	Alpha
0.80010	112	112	224	1.00	3.00	0.050
0.80084	199	199	398	1.00	4.00	0.050
0.80590	29	29	58	2.00	3.00	0.050
0.80590	51	51	102	2.00	4.00	0.050
0.82409	14	14	28	3.00	3.00	0.050
0.80486	23	23	46	3.00	4.00	0.050
0.81316	8	8	16	4.00	3.00	0.050
0.82409	14	14	28	4.00	4.00	0.050
0.85055	6	6	12	5.00	3.00	0.050
0.81383	9	9	18	5.00	4.00	0.050
0.80153	4	4	8	6.00	3.00	0.050
0.84086	7	7	14	6.00	4.00	0.050

NOTE: Once the treatment for the clinical trial is unblinded, if DSI is unchanged or worsens by 1 in the placebo arm, then one could detect as little as a 1 or 2 point reduction in DSI by selonsertib in the treatment arm.

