**Statistical Methods:**

We will determine the utility of the Disease Severity Index (DSI) from the HepQuant SHUNT test to monitor liver disease and treatment effects by measuring liver function and physiology. We propose a three-step analytical process to achieve this goal. First, without knowledge of treatment arm, we will track DSI and the change in DSI,  $\Delta$ DSI, from baseline to on-treatment and follow-up timepoints. Second, we will apply separate survival models to evaluate  $\Delta$ DSI as a continuous variable and a 2 point or more change in DSI as dichotomous variable in the prediction of changes in other tests or models of liver disease severity and clinical outcomes. In HCV, an increase in DSI of 2 or more has been associated with disease progression; and, a decrease in DSI of 2 or more has been associated with improvement after viral clearance. Third, once the treatment arms have been unblinded we will evaluate if the use of the HepQuant SHUNT test and DSI identify a treatment effect in the combined cohort of NASH F3 plus NASH F4; and we will compare DSI to the primary measures of efficacy in each of the clinical trials. In terms of DSI, a treatment effect will be defined from the difference between the  $\Delta$ DSI of the treatment arm versus the  $\Delta$ DSI of the placebo arm. The significance of this difference will be evaluated using a two-sided t-test. Furthermore, we will link treatment effect defined by DSI to effects of treatment on other tests and clinical outcomes (bleeding from varices or portal hypertensive gastropathy, ascites, encephalopathy, SBP, progression to cirrhosis, and patient mortality or liver transplantation). We will use both generalized estimating equations (GEE) and profile analysis – profile of DSI between treatment and placebo groups at each time point – for additional primary endpoint analyses.

We will also determine the ability of baseline DSI, performed prior to treatment, to assess the severity of liver disease by: 1. correlation with other baseline tests of liver disease severity; and, 2. prediction of risk for future clinical outcome.

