### 8.2.3 Statistical Considerations

Our Primary Objective is to determine the utility of the Disease Severity Index (DSI), derived from the HepQuant SHUNT test, to monitor liver disease and treatment effects. We propose a three-step analytical process to achieve this goal:

- First, without knowledge of treatment arm and for the group of subjects as a whole, we will track DSI and the change in DSI,  $\Delta$ DSI, from baseline to on-treatment and follow-up timepoints.
- Second, we will apply separate survival models to evaluate  $\Delta$ DSI as a continuous variable and a 2 point or more drop in DSI as dichotomous variable in the prediction of changes in other tests or models of liver disease severity and clinical outcomes.
- Third, after unblinding the study and completion of Gilead's analysis of the main clinical trial, we will make request of Gilead for allocation code to determine if there is a treatment effect, by comparing the difference between the  $\Delta$ DSI of the treatment arm versus the  $\Delta$ DSI of the placebo arm. The significance of this difference will be evaluated using two-sided t-tests and survival models.

Due to short enrollment period, only 5 STELLAR 3 and 4 STELLAR 4 subjects were enrolled into HQ-SHUNT-1701. STELLAR 3 and STELLAR 4 had two treatment arms (6 and 18 mg/d doses) and one placebo arm. Of the 9 subjects enrolled in HQ-SHUNT-1701, we would project that 6 would have been treated with selonsertib and 3 would have been taking placebo. Enrollment criteria, diagnosis, and F3/F4 stage of NASH is identical between the STELLAR studies and Gilead 454-4378. For the final analysis of treatment effects, once the code on all treatment arms from all studies is unblinded the projected 6 cases enrolled in HQ-SHUNT-1701 on selonsertib treatment from STELLAR studies will be added to the cases from Arm C of 454-4378 (selonsertib monotherapy) and the projected 3 cases enrolled in HQ-SHUNT-1701 on placebo from STELLAR studies will be added to the cases from Arm F (placebo) of the 454-4378 study.

Furthermore, we will link treatment effect defined by the change in DSI to effects of treatment on other tests and clinical outcomes (bleeding from varices or portal hypertensive gastropathy, ascites, encephalopathy, SBP, progression to cirrhosis, and

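### The sample-size table assumes a one-sided 5% test but the plan specifies a two-sided t-test, so 60 subjects do not give 80% power for a 2-point DSI difference

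*Combined protocol and SAP*

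**What the plan says.** Section 8.1 says that earlier serial studies allowed "defining an average standard deviation for" ΔDSI, and gives it as 3.5. It then introduces a 12-row table as showing the "sample sizes required to detect a range of changes in DSI at 80% power or higher". The rows use SDs of 3 and 4 only, equal arms, and alpha 0.050 with no statement of sidedness. The row closest to 60 subjects for a 2-point difference reads "0.80590 29 29 58 2.00 3.00 0.050" (power, N1, N2, N, ΔDSI, σ, alpha).

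The section then draws on the table to name a total: "A sample size of 60 total subjects (N in following table), well below the size of our projected number of evaluable NASH patients". It describes the power at this number as sufficient for a between-arm gap of 2 to 3 points. A closing note adds that, if placebo DSI is stable or worsens by 1, a reduction of only 1 or 2 points on selonsertib could be detected.

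The test itself is specified in two places. The Synopsis says: "The significance of this difference will be evaluated using a two-sided t-test". Section 8.2.3 says: "The significance of this difference will be evaluated using two-sided t-tests and survival models". No section specifies a one-sided test.

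Section 8.2.3 also fixes which subjects enter the final treatment comparison. The projected 6 STELLAR subjects on selonsertib "will be added to the cases from Arm C of 454-4378 (selonsertib monotherapy"), and the projected 3 on placebo join Arm F. Total enrolment across all trials is capped at 100.

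**The concern.** The power values in the table are higher than a two-sided 5% test would give at those sample sizes. If the table was computed one-sided, every N in it is too small for the planned analysis.

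The SD adds a separate problem. The text names 3.5 as the value to size with, but the 2-point claim at about 60 subjects matches only the SD 3 row. The SD 4 row for the same difference needs 102.

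Two points is also the change the plan itself uses as its dichotomous cut-off in the survival models, so it is the difference a reader will expect the study to detect. If the true power at 2 points is well below 80%, a non-significant DSI comparison says little about either the test or the drug. A reader relying on Section 8.1 could take it as evidence against one of them.

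**Working it through.** **Inputs.** From Section 8.1: alpha 0.05, target power at least 80%, equal arms, SD 3 and 4 (table) and 3.5 (text), total N of 60 taken as 30 per arm. From the Synopsis and Section 8.2.3: two-sided t-test.

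**Formula.** For a two-sample t-test with common SD σ and difference δ:

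- df = n1 + n2 − 2
- noncentrality λ = δ / (σ√(1/n1 + 1/n2))
- one-sided power = P(T > t(0.95, df)), with T noncentral t(df, λ)
- two-sided power = P(T > t(0.975, df)) + P(T < −t(0.975, df))

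**Step 1: reproduce the plan's figure.** For 29 per arm, δ = 2, σ = 3: df = 56 and λ = 2 / (3√(2/29)) = 2.539.

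- One-sided, critical value 1.673: power 0.80590, which is the tabulated value.
- Two-sided, critical value 2.003: power 0.704.

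**Step 2: all rows.**

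| δ | σ | n per arm | Stated power | One-sided | Two-sided | Total N, two-sided 80% (stated) |
|---|---|---|---|---|---|---|
| 1 | 3 | 112 | 0.80010 | 0.80010 | 0.700 | 286 (224) |
| 1 | 4 | 199 | 0.80084 | 0.80084 | 0.701 | 506 (398) |
| 2 | 3 | 29 | 0.80590 | 0.80590 | 0.704 | 74 (58) |
| 2 | 4 | 51 | 0.80590 | 0.80590 | 0.706 | 128 (102) |
| 3 | 3 | 14 | 0.82409 | 0.82409 | 0.721 | 34 (28) |
| 3 | 4 | 23 | 0.80486 | 0.80486 | 0.701 | 58 (46) |
| 4 | 3 | 8 | 0.81316 | 0.81316 | 0.699 | 20 (16) |
| 4 | 4 | 14 | 0.82409 | 0.82409 | 0.721 | 34 (28) |
| 5 | 3 | 6 | 0.85055 | 0.85055 | 0.740 | 14 (12) |
| 5 | 4 | 9 | 0.81383 | 0.81383 | 0.702 | 24 (18) |
| 6 | 3 | 4 | 0.80153 | 0.80153 | 0.657 | 12 (8) |
| 6 | 4 | 7 | 0.84086 | 0.84086 | 0.731 | 18 (14) |

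The one-sided calculation matches every row, and each tabulated n is the smallest that reaches 80% one-sided. The two-sided calculation matches none.

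**Step 3: the 60-subject statement, 30 v 30.**

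| σ | Two-sided power, δ = 2 | Two-sided power, δ = 3 | δ detectable at 80% | Total N for δ = 2 |
|---|---|---|---|---|
| 3 | 0.719 | 0.968 | 2.21 | 74 |
| 3.5 | 0.586 | 0.904 | 2.57 | 100 |
| 4 | 0.478 | 0.815 | 2.94 | 128 |

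Sidedness is not the only cause. Even one-sided, power for 2 points at SD 3.5 is 0.706.

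**Step 4: the closing note.** Read generously, as a 2-point gap between arms, the note fails at N = 60 as in Step 3. Read as a 1-point gap, two-sided power at SD 3.5 is 0.29 even with all 100 subjects split 50 v 50.

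**Step 5: the comparison in Section 8.2.3 (illustrative).** The documents do not give the allocation in GS-US-454-4378. Arm labels running to F imply at least six arms. I assume that the cap of 100 is filled, that the 91 subjects outside STELLAR are split evenly, and that SD is 3.5.

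- Six arms: 91/6 ≈ 15, so 15 + 6 = 21 v 15 + 3 = 18. Two-sided power is 0.41 for 2 points and 0.74 for 3, and the 80% detectable difference is 3.2.
- Seven arms: 91/7 = 13, so 13 + 6 = 19 v 13 + 3 = 16. Power is 0.37 and 0.69, and the detectable difference is 3.4.

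**The case against.** The strongest points on the other side are these.

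- **The wording is softer than 80% at 2 points.** The text speaks of sufficient power for 2 to 3. At 3 points, 30 v 30 does give 0.82 to 0.97 two-sided, and at SD 3.5 the 80% threshold of about 2.6 lies inside the stated range. This stands as a limit: only the lower end fails. But the sentence follows directly on a definition of the table as 80% power or higher, and the 2-point end corresponds to the N = 58 row, so the reader is told 80% at 2 points.
- **SDs of 3 and 4 bracket 3.5, and the table openly shows 102 for 2 points at SD 4.** This is fair. The missing SD 3.5 row is an omission, not an arithmetic error. The summary sentence nevertheless relies on the favourable row.
- **The Arm C v Arm F figures rest on an assumed allocation and a filled cap.** This is correct. They are illustrative and should not be written into the protocol as facts. The sidedness finding does not depend on them.
- **The t-test is one part of the primary objective.** GEE, profile analysis and two analyses blind to treatment are also planned, and 100 is a ceiling, not a number derived from this table. This is true, but Section 8.1 powers only the two-arm difference, and that is the calculation in error.
- **A one-sided test might be defensible**, because Section 2.1 expects a directional result. It would remove the inconsistency only if the plan adopted and justified it, and it would still leave 0.71 power for 2 points at SD 3.5.

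**Conclusion.** The table is wrong for the planned analysis. That conclusion needs no assumption beyond the documents' own numbers: the power column is one-sided, the test is two-sided, and every row falls short of 80%.

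The 60-subject claim is unsupported at 2 points for each SD the document mentions and supported at 3 points, assuming 30 v 30 with no loss of evaluable subjects. At SD 3.5 a 2-point difference would need every one of the 100 permitted subjects, all evaluable and in a single two-arm comparison. That cannot be squared with describing 60 as comfortably below the projected evaluable number.

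The shortfall for the comparison actually planned is probably larger, but its size depends on an allocation the documents do not give. Correction is required.

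**What to change.** 1. Recompute the Section 8.1 table for the two-sided t-test at alpha 0.05, state the sidedness in the table, and add SD 3.5 rows. The alternative is to justify a one-sided test and change the Synopsis and Section 8.2.3 to match.
2. Replace the 60-subject sentence with: 30 v 30 gives 80% two-sided power for a difference of about 2.6 at SD 3.5, and a 2-point difference needs 100 subjects in the two compared arms.
3. State the power and detectable difference for Arm C plus STELLAR selonsertib against Arm F plus STELLAR placebo, using the real allocation and expected evaluable numbers. The range of about 3.2 to 3.4 points above is a placeholder under even allocation.
4. Revise the closing note on 1- to 2-point reductions to agree with the corrected figures.

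The cost is a correction to one table and a few sentences. The stated figures become less favourable, and enrolment does not change.
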